Protocol Title: The Role of HMGB-1 in Chronic Stroke

Principal Investigator: [name]

Sub-Investigator: [name]
[name]

Study Coordinator: [name], MS

Introduction

The acute pathophysiology of stroke depends on the innate immune response that begins in a clotted vessel and overwhelms the perivascular and parenchymal affected regional anatomic sector with all of the effector molecules arising from mostly pro-inflammatory cascades. The chronic pathophysiology of stroke is less clear as the innate inflammatory response fades and matures into an adaptive immune response. We want to investigate whether the pro-inflammatory circumstances extend over longer time in patients with stroke by measuring a candidate serum cytokine – HMGB-1 – that is secreted long after an initial insult, causes organ damage, and can be inhibited. Building on the work of the [name] lab here at Feinstein on sepsis [1], and working in the [name] lab we have developed new information about the effect of HMGB-1 on the brain. **We hypothesize that persistent HMGB-1 serum levels in patients with stroke retard functional recovery.** A first step in the test of this hypothesis is to gather serum data in patients with stroke longitudinally. Because we will have collected timed serum samples and stored them in the bio-repository at Feinstein, the hypothesis will be enriched by reexamining the serum samples for other known cytokines, other danger associated pattern molecules (DAMP), and growth factors that may also contribute to a prolonged inflammatory state for some stroke victims. If it turns out that in some patients the inflammatory condition wanes soon after the acute stroke then it will be important to determine the functional outcome compared to those in whom the inflammatory condition persists. While not in the scope of this particular protocol, we have long experience using modern interactive robotic techniques to measure and also to enhance motor function in patients recovering from stroke [2, 3], as our long term goal is to influence future stroke-rehabilitation practice.

Specific Aims

As a first step in achieving a long-term goal to improve stroke recovery, we will determine when and how long the circulating HMGB-1 levels are elevated in patients with stroke. We will also compare the cytokine levels of individuals after stroke with those of health, age-matched controls. We will:

1. Measure the levels of HMGB-1 in patients with acute stroke. We currently have the tools available to measure the levels of HMGB-1 in humans by ELISA (IBL-International, Toronto; ST51011).

2. Measure the level of cytokines, DAMPs and growth factors downstream from HMGB-1 secretion. If we find that levels of HMGB-1 are elevated after stroke, we will assay the levels longitudinally over a 3 month period. We will return to the bio-repository to assay samples for IL-1, IL-6, IL-8, IL-10, TNF and BDNF, all molecules known to be stimulated by HMGB-1 secretion [4, 5], and for which there are well developed ELISA protocols and further there are well developed assays for the Meso-Scale Diagnostics (MSD: Gaithersberg,MD) in the [name] lab. The interleukins and TNF are well known cytokines involved in pro-inflammatory response. BDNF is a growth factor involved in repair [6, 7]. As HMGB-1 levels are negligible in normal healthy volunteers we do not expect that patients with acute stroke will have low levels. While there is some support to use a published lower level of 20 ng/ml as a cutoff for further cytokine and growth factor analysis [5], it seems prudent under the circumstances of the current lack of knowledge about the longitudinal characterization of cytokines and growth factors after stroke to

analyze the blood samples over time for HMGB-1 and for the cytokines and growth factors mentioned.

3. Compare the level of cytokines individuals with acute stroke with those of age-matched, healthy controls. In order to establish baseline cytokine levels, we will collect serum samples from healthy, age-matched controls and assay them for HMGB-1, IL-1, IL-6, IL-8, IL-10, TNF, and BDNF. We predict that cytokine levels will be negligible in healthy subjects and their samples will serve as a control for individuals post-stroke.

Background and Significance

Stroke, cerebrovascular accident, is the leading cause of brain injury and the leading cause of permanent disability. Over 800,000 people per year are afflicted with stroke in the US, and despite effective prevention campaigns like smoking cessation and blood pressure control, and medical treatments that have decreased the mortality from acute stroke, well over 5 million survivors now have permanent disability at a cost of billions spent for chronic care [8]. Post stroke treatment depends on supportive care and the imperfect spontaneous recovery of function abetted by compassionate rehabilitative efforts. Recent pre-clinical work [7, 9, 10] has provided a rationale that demonstrates that neuroplastic changes that underlie recovery might be improved by increased intensity of motor activity during therapy. Our group has been on the forefront of this development [11-14]. We have developed and used interactive robotic devices to deliver adaptive motor training that progressively increases training intensity, provides just-enough challenge to keep the patient focused and interested, and, importantly, has demonstrated that patients undergoing these robotic treatment protocols have significantly improved motor function [2, 3].

Ischemia and reperfusion triggers innate immune response first in the compromised vessel, in the perivascular and the brain parenchymal space. Early innate immune events follow clotting, platelet-leucocyte aggregation, complement activation [15, 16], increased arachidonic acid metabolites and reactive oxygen species [17, 18], and cytokine release, especially IL-1 [19-21]. Up-regulation and release of selectins, integrins [22, 23], proteases (like matrix metalloproteinases) [24, 25], and loss of NO (nitric oxide) [26] provide platforms for leucocyte adhesion, rupture of the blood-brain barrier, and matrix proteolysis. Mast cell degranulation releases histamine and additional proteases increasing signals for inflammatory cell migration to blocked and leaky vessels. The parenchyma of the brain fares no better; cytokines and chemokines [27-30] disrupt the microglia-neuron communication and TNF, depending on its source [31-34], provokes continued pro- but also insufficient anti-inflammatory signals and ATP is released, extracellular glutamate rises and cells die. Left out of this brief highlight summary of the early response of the immune system to stroke is the complete list of activated and secreted cytokines; including IL-6, IL-10, IL-12, IL-17, IL-18, IL-20, IL-23 [35-41], growth factors [42-44], and enzymes [26, 45, 46]. Persistent cell death initiates a new phase of the immune physiology the adaptive response. Altering these complex cascades will be a challenge. Furthermore, any intervention will require a certain immediacy and timeliness that currently exceeds standard and even premium health care delivery systems. More likely effective interventions will come from elucidation of the ongoing inflammatory response.

Interferon and TGF sensitize and prime T cells and antigen presenting cells (dendritic cells), and danger associated pattern molecules (DAMP) like HMGB-1 which in turn activate toll like receptors (TLR). Recent work on the humoral immune response has focused on the increased

production of antigen presenting cells (APCs), lymphocyte infiltration and the expression of co-stimulatory molecules like CD80 [47]. Some experimental pre-clinical evidence suggests that T- and B- cell deficient mice have reduced lesion size after exposure to experimental stroke [48], and progress in delineating mechanism has ruled against antigen recognition, or T-cell receptor co-stimulation, or thrombus formation [49]. But the mechanism for stroke exacerbation caused by humoral and adaptive immune response is not clear. Nor is it clear that the adaptive response is only to exacerbate the ischemia, as experiments with regulatory T cells and IL-17 for example, demonstrate an anti-inflammatory response [50, 51]. Lurking in the literature though, is the persistent rise of HMGB-1 levels and pre-clinical experiments show the rise continues for weeks to months. We believe this persistent pro-inflammatory signal represented by increased serum HMGB-1 needs investigation.

Progress Report/Preliminary Studies

To that end, it is important to note that the medicine group at Northwell, under the guidance of the [name] group at Feinstein, has assayed the HMGB-1 levels in serum samples collected from some patients with brain and cardiac ischemia [52, 53]. Their data show that collection of acute blood samples in the Northwell is possible and, importantly for the purpose of this protocol that the some stroke and cardiac patients have elevated HMGB-1 serum levels hours after the ictus (**Fig 1A & B**). The variable serum levels of HMGB-1 are due to different assays, currently there is a standard ELISA kit for HMGB-1 analysis in the serum (IBL-International, Toronto; ST51011). Of note, the levels of HMGB in serum from age-matched healthy controls were typically less than 20ng/ml of HMGB-1 [5]. Importantly the level of HMGB-1 increased significantly with patients who had their blood sampled after longer times from the onset of their stroke (**Fig 1C**). The progression and persistence of HMGB-1 is not known in the clinical literature, although [name]'s lab has demonstrated that HMGB-1 levels persist in sepsis experiments for weeks (see **Fig 2**).

[figure not shown]

Fig 1A. Stroke patients (N=8) had significantly higher HMGB1 serum concentrations than controls. Patients were included into the study within 24 h after onset of symptoms.
Fig 1B. Stroke patients (N=7) had significantly higher HMGB1 serum concentrations than controls.
Fig 1C. HMGB serum levels rise as a function of symptom onset. Serum from patients with myocardial infarction (N=9) and cerebral ischemia (N=7) obtained on arrival in the emergency department and correlated with the historical onset of symptoms ($R^2= 0.49$, $P<0.01$).

[figure not shown]
[figure not shown]
[figure not shown]

Fig 2. Animals exposed to severe sepsis (standard cecal ligation and puncture; N=50) demonstrate persistent elevation of HMGB-1 serum measurements.

In an animal model we have been exploring the effect of severe sepsis using a standard stress of cecal ligation and puncture (CLP) on the brain. HMGB1 levels do not rise immediately following CLP but an elevation is sustained for several weeks, making it an ideal therapeutic target. These preliminary results support a rationale for the proposed protocol.

Sepsis is a common clinical problem with a 30% acute mortality, but the survivors do not return to work and sustain loss of both cognitive function and immunocompetence [54-56]. To understand the persistent cognitive impairment in sepsis survivors, we subjected mice to sepsis induced through cecal puncture and ligation (CLP). At 4 weeks following CLP sepsis, mice displayed a loss of long term potentiation (LTP) in hippocampal slice preparations; a measure that can be taken as a loss of synaptic plasticity (**Fig3A**). Also on histologic analysis these animals demonstrated a loss of dendritic arborization and spine density in CA1 neurons of the hippocampus (**Fig 3B**). To ask whether these deficits were a consequence of systemic immune activation, we measured the performance of mice treated with severe sepsis and sham exposed mice on a clock maze. The latency of a mouse's escape is generally thought to depend on memory, and is further thought to be mediated in part by hippocampal neuronal function. **Fig 4A** depicts the performance of mice exposed to severe sepsis and demonstrating memory impairment. In another experiment (**Fig4B**), we treated mice exposed to CLP sepsis for one week with antibody to the inflammatory cytokine HMGB1, beginning one week following CLP. Antibody-treated mice displayed partial improvement in cognition, demonstrating that prolonged systemic inflammation contributes to the post-sepsis cognitive decline and suggesting a therapeutic strategy for neuroprotection in sepsis survivors.

We know that overwhelming sepsis and stroke are different conditions and impose a number of different stresses on the patient/experimental animal. However, the two conditions share some molecular mediators; especially HMGB-1. Also both stroke and sepsis cause immediate rise in TNF and IL-1, sentinels in the innate immune system. High levels of these cytokines persist for hours to days in mice, but return to baseline by 3 days. This first wave of cytokines is followed by a later but more sustained elevation of HMGB1. Increased levels of HMGB1 persist for weeks with a return to baseline levels in mice at around eight weeks following the initial insult. This information is not entirely clear in animal stroke models or in patients with stroke, a void that this protocol intends to correct.

4 WEEKS AFTER EXPOSURE TO SEPSIS OR SHAM

Fig 3A. Hippocampal neuron circuits in a slice preparation from animals exposed to severe sepsis (CLP) procedure fail to generate and maintain LTP. Hippocampal neuron circuits from control (sham) animals generate normal LTP. **Fig 3B.** Using Golgi staining techniques in which random but entire neurons are filled with peroxidase positive material, animals exposed to severe sepsis (CLP) lose dendritic arborization and, on higher magnification, demonstrate significantly decreased spine density compared to the hippocampus of sham (control) treated animals (1.11 ± 0.29 spines/ μ vs. 0.54 ± 0.21 spines/ μ ; $P < 0.001$).

[figure not shown]

Fig 4A. Animals exposed to severe sepsis (CLP) demonstrated impaired learning in a clock maze. **Fig 4B.** This impairment was altered by treating the animals with a neutralizing anti-HMGB-1 antibody.

Research Design and Methods

We will obtain blood samples from 100 consecutive patients with ischemic or hemorrhagic stroke admitted to the Northwell stroke service. As we are interested in assay of HMGB-1 from the time from stroke, the admission sample timing with respect to stroke will be noted and we will obtain subsequent blood samples at 7, 14, 30 and 90 days after the time that the stroke occurred. So if the patient comes in 24- or 48-hours after the onset of symptoms, we will collect the admission sample and collect the 7-day sample 6 or 5 days after admission respectively. Given the challenges of collecting samples within a 24 hour time period, the collection window will be extended such that day 7 and day 14 samples will be collected plus or minus one day of the target (e.g. between day 6-8 or day 13-15, respectively) and day 30 and day 90 samples will be collected plus or minus 7 days of the target (e.g. between day 23-37 and day 83-97, respectively). Each of the 5 samples will be 4 cc each (green top tube). We will also obtain a one-time DNA sample, via the collection of a 10cc lavender tube (EDTA) at the time of the first sample collection. If this is not possible we will collect this sample at the time of a subsequent research blood sample collection. The total volume of blood drawn for each study subject will be no more than 30 cc over the duration of the study. Additionally, we will collect a one-time blood sample from up to 30 healthy, age-matched controls. Control subjects will be NSLIJHS employees, members of the local community recruited with the Northshore Recruitment Registry and GAP Registry recruitment tools, and enrolled subjects' family members recruited by the Research Coordinator and Principal Investigator. Each control sample will be 4cc total (green top tube)

The blood will be centrifuged and prepared for HMGB-1 analysis by NS-LIJ Biorepository staff. If we miss sample collection across the 7, 14, 30, and 90 day time points the available collected samples from a subject will be analyzed. We will measure HMGB-1 and if the levels are elevated (>20ng/ml) we will return to the banked samples in the bio-repository to repository to assay samples for IL-1, IL-6, IL-8, IL-10, TNF and BDNF, all molecules known to be stimulated by HMGB-1 secretion [4, 5].

The following data will be collected for each subject with stroke:

- Age (at time of stroke)
- Gender
- Stroke risk factors (history of hypertension, smoking, estrogen supplements)
- Concurrent infections (at time of stroke)
- Stroke type (ischemic or hemorrhagic)
- Stroke location
- Stroke severity (NIH Stroke Scale)
- Stroke outcome (Rankin scale) – measured at admission & discharge
- Contact information
- Medical record number

Inclusion criteria:

- All patients admitted to the stroke service at Northwell will be eligible for inclusion in this pilot study.
- Patients \geq 18-years of age

Exclusion criteria:

- Patients <18-years of age

The following data will be collected for each control subject:

- Age (at time of stroke)
- Gender
- Stroke risk factors (history of hypertension, smoking, estrogen supplements)
- Concurrent infections (at time of stroke)
- Contact information

Inclusion criteria:

- Patients \geq 18-years of age
- No report of stroke risk factors (hypertension, smoking, estrogen supplements) or concurrent infections during screening at time of participation.

Exclusion criteria:

- Patients <18-years of age
- Report of stroke risk factors or concurrent infections during screening at time of participation.

Because of the collaborative efforts of the Department of Neurology and the Physical Medicine and Rehabilitation groups we will be able to track the patients from the acute care facility to the rehabilitation units. We know that the combined admissions to the stroke units at the two facilities are nearly 900 patients per annum. We also know that the patients often stay within the greater Northwell Health System and that over 700 patients with stroke are admitted to the rehabilitation units.

Blood sampling for acute stroke subjects will take place on the subjects' in-patient units during their stay in Northwell Health System. We expect, as the average length of stay is 10 days, to collect an admission and day 7 sample. Many patients with stroke are transferred to the rehabilitation service and we expect to collect blood samples for day 14 and 30 on those services. The average length of stay for a patient with stroke on an in-patient rehabilitation unit is 30 days. We are set up in the CRC to collect the 90 day sample and the control subjects' samples. We will ask patients to return to the CRC for this sample collection.

Banking of samples for future use:

The Tissue Donation Program (TDP) collects and stores biological samples and associated clinical data as a resource for investigators in the Northwell Health System. Through the development and implementation of tissue specific sub-protocols, these materials may be available to the larger biomedical community. A portion of each blood sample collected for this study will be stored by the TDP and made available for future research according to TDP established procedures.

Plasma will be stored from each blood sample collected. DNA will be isolated and stored once on each patient with stroke at the time of the first blood collection. If for some reason this is not possible, a DNA sample will be isolated from the next available blood sample.

These samples stored by the TDP can be shared by other investigators who submit protocol for use of stored samples to the TDP's Committee for Participant Protection (COPP). Once approved by the COPP, stored samples and associated clinical data can be distributed to the investigator in a completely de-identified fashion. Investigators receiving samples will not have access to the link between a bar coded label and subject identity.

Statistical Considerations and Data Analysis

Specific Aims:

1. Measure the levels of HMGB-1 in patients with stroke. Because the level of HMGB-1 in healthy control subjects is negligible and because survivors of sepsis had levels of HMGB-1 < 20 ng/ml, we believe it is reasonable to assume that levels above 20ng/ml are not normal [5]. Also we are collecting longitudinal samples and we expect that if the pro-inflammatory condition clears in these patients with stroke the HMGB-1 level will fall below 20 ng/ml if not lower.

2. Measure the level of downstream pro-inflammatory molecules and growth factor. We will measure IL-1, IL-6, IL-8, IL-10, TNF and BDNF, all molecules known to be stimulated by HMGB-1 secretion. If we find that HMGB-1 is elevated we expect to find elevations in the other

molecules. If HMGB-1 is not elevated it will be important to measure the serum level of the other cytokines to insure that some other pathophysiology of stroke and stroke recovery is not also involved in activating cytokines. The serum growth factor BDNF level may change in an alternate direction.

Endpoint Variables:

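### The Methods make the six downstream assays conditional on HMGB-1 above 20 ng/ml, against the conclusion of Aim 2 and the statistical section, and do not name the unit of the condition

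*Combined protocol and SAP*

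**What the plan says.** The combined protocol and SAP addresses the downstream assays in several places.

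- **Research Design and Methods:** "We will measure HMGB-1 and if the levels are elevated (>20ng/ml) we will return to the banked samples in the bio-repository", followed by the list IL-1, IL-6, IL-8, IL-10, TNF and BDNF.
- **Specific Aims, Aim 2, opening:** "If we find that levels of HMGB-1 are elevated after stroke, we will assay the levels longitudinally over a 3 month period".
- **Specific Aims, Aim 2, conclusion:** it grants that "there is some support to use a published lower level of 20 ng/ml as a cutoff for further cytokine and growth factor analysis". It then judges it prudent, given how little is known about the time course after stroke, to "analyze the blood samples over time for HMGB-1 and for the cytokines and growth factors mentioned".
- **Statistical Considerations, Specific Aim 2:** the six analytes will be measured. If HMGB-1 is not elevated, the other cytokines are still important, as a check that some other process is not driving them.
- **Specific Statistical Aims and Statistical Analysis:** HMGB-1 and the six analytes are to be evaluated in 100 patients over three months, with repeated-measures analysis of HMGB-1 and the cytokines as the main analysis.
- **Aim 3, controls:** "we will collect serum samples from healthy, age-matched controls and assay them for HMGB-1, IL-1, IL-6, IL-8, IL-10, TNF, and BDNF", with no condition attached.

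**The concern.** The Methods sentence is an operating instruction: it tells the laboratory when to go back to the bank. The statistical section describes a dataset that exists only if the laboratory goes back whatever the HMGB-1 result. Staff following one and an analyst following the other could end up with different data.

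The condition is also placed on one of the variables under study. Statistical Considerations, Specific Aim 1, expects HMGB-1 to drop below 20 ng/ml in patients whose inflammation clears. If the condition worked sample by sample, a patient who clears would stop contributing cytokine values at that point. Late cytokine averages would then describe only patients still above the threshold. The plan could not say whether the cytokines fell along with HMGB-1, which is part of what the repeated-measures description is for. Paired analyses of HMGB-1 with TNF or IL-1 would likewise use only high-HMGB-1 samples.

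**Working it through.** There is no power or sample-size figure to reproduce: the sample is one of convenience. The check has two parts.

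**1. The texts side by side**

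| Place | Are downstream assays conditional on HMGB-1? | Unit stated? |
|---|---|---|
| Research Design and Methods | Yes, above 20 ng/ml | No |
| Aim 2, opening | Longitudinal assay follows elevation; which analytes is unclear | No |
| Aim 2, conclusion | No; threshold considered and set aside | Not needed |
| Statistical Considerations, Specific Aim 2 | No; wanted also when HMGB-1 is not elevated | Not needed |
| Specific Statistical Aims | No; 100 patients | Not needed |
| Aim 3, controls | No | Not needed |

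The sharpest conflict is between the first and fourth rows. The statistical section asks for the cytokines in exactly the case where the Methods condition does not trigger them.

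**2. What each unit would cost**

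Inputs from the documents: 100 patients, 5 draws each (admission, days 7, 14, 30 and 90), 6 conditional analytes. Complete collection is assumed, so these are upper limits; the Methods allow for missed draws.

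- Planned patient samples: 100 × 5 = 500. Conditional values: 500 × 6 = 3,000.
- **Per sample.** Each 10% of samples at or below 20 ng/ml removes 0.10 × 500 = 50 samples, or 50 × 6 = 300 values. The share is not in the documents. Over an assumed range of 10% to 70%, the loss is 300 to 0.70 × 500 × 6 = 2,100 of 3,000 values. If 25%, 50% or 75% of patients (assumed) have cleared by day 90, then 75, 50 or 25 of 100 day-90 values remain per analyte. At most that many patients have a complete five-point cytokine series.
- **Per patient.** Each 10% of patients never above the threshold removes 10 patients, or 10 × 5 × 6 = 300 values. These are the patients in whom Statistical Considerations, Specific Aim 2, wants to look for another mechanism.
- **Cohort.** No values are lost if the condition is met, and all 3,000 if it is not. The second case again contradicts the statistical section.

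HMGB-1 is to be measured whatever happens to the other assays. A joint model of HMGB-1 and each cytokine could therefore recover part of a per-sample loss. The plan specifies no such model. It would also have to extrapolate the relation below 20 ng/ml, where no cytokine data would exist.

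**The case against.** The strongest reply is that the plan largely answers the point itself. The Methods say *if*, not *only if*; the statistical section supplies the other branch; and Aim 2 reasons its way to assaying everything. The staged wording in Aim 2 and in Statistical Methods, where the study first asks whether levels are raised and then describes their time course, suits a decision taken once for the whole cohort. Aim 2 also says of the stroke group that "we do not expect that patients with acute stroke will have low levels". On the cohort reading nothing is lost once the condition is met, and no passage states a per-sample rule.

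Much of this stands, and the cohort reading is plausible. But no passage states it either, and Aim 2 itself describes 20 ng/ml as a cutoff for further assays, so reading the Methods sentence as a gate is fair. The conflict with the statistical section also remains on the cohort reading if HMGB-1 is not elevated.

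It also stands that the analysis is primarily descriptive, the paired analyses are exploratory, and plasma is stored from each sample. These limit the harm. They do not reconcile the text.

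**Conclusion.** The point holds as an inconsistency in the current text with a consequence that depends on an unstated unit. Confidence is high in the conflict and lower in the harm. The loss runs from nothing (cohort, condition met) to 300 values for each 10% of samples or patients excluded. Those figures rest on complete collection and on shares the documents do not give. Whether HMGB-1 itself is elevated after stroke is unaffected.

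A reader might infer more, and the documents do not support it:

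- *That late cytokine data will be lost.* This follows only on a per-sample reading and only for patients who clear.
- *That the control comparison collapses because healthy levels are usually below 20 ng/ml.* Aim 3 assays controls for the full panel without condition, in both the Specific Aims and the statistical section.
- *That the HMGB-1/cytokine correlations would be distorted by a known amount.* Neither size nor direction can be derived, and the method cited for pairs is within-subject correlation, which a pooled coefficient would not represent.
- *That Fig 1C shows early samples falling below the threshold.* A correlation with time from onset says nothing about the share at or below 20 ng/ml.
- *That the opening of Aim 2 clashes with the repeated-measures plan.* Statistical Methods carries a similar staged condition, so the clear mismatch is between that opening and Aim 2's own conclusion.

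**What to change.** Before any downstream assay is run:

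1. Delete the 20 ng/ml condition from Research Design and Methods.
2. Bring the opening of Aim 2 into line with its conclusion.
3. State once that HMGB-1 and the six other analytes are assayed in every available patient sample and every control sample.
4. Keep 20 ng/ml only as a descriptive cutoff for reporting HMGB-1.

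If resources require a condition after all, name its unit, say that controls are exempt, reconcile it with Statistical Considerations, Specific Aim 2, and report how many samples it excluded at each time point.

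The cost is a wording change plus assays on at most 500 patient and 30 control samples, which Aims 2 and 3 and the statistical section already imply. The documents give neither the assay budget nor the volume stored per sample, and stored material may also be shared with other investigators. The sponsor should confirm that both budget and volume cover seven analytes.
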